8.1 Patient inclusion

Patients will be identified as eligible by local investigators using methods specific to the centre, however this will likely involve published operating lists and emergency theatre bookings. All eligible patients will be included if possible.

9 Data

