Additionally, the lead for each site will submit, via the on-line REDCap system, the study week that site has selected (from one of weeks commencing 1st, 8th, 15th, 22nd or 29th November), the total number of eligible procedures for each 24 hour period of the study, and the list of all local investigators involved in the study (to enable production of certificates to demonstrate involvement as well as to allow naming of all collaborators on any manuscripts arising from the study). The site details data capture form is provided in *Appendix 3*.

All investigators and any other individuals contributing to the study will be required to comply with the Data Protection Act 2018 and the NHS code of confidentiality.

Data to be collected:

- Site (automatically populated dependent upon the login credentials of the local investigator)
- Day of the study
- Age of patient (grouped into 18-39, 40-59, 60-79 and \geq 80 years)
- Sex of patient
- American Society of Anesthesiologists (ASA) physical status
- Patient body mass index (BMI), grouped into underweight (< 18.5 kg/m²), normal (18.5 24.9 kg/m²), overweight (25.0 29.9 kg/m²), class 1 obesity (30.0 34.9 kg/m²), class 2 obesity (35.0 39.9 kg/m²), class 3 obesity (>= 40.0 kg/m²)
- Surgical urgency (elective; expedited; urgent; emergency)
- Start time of procedure (first set of observations entered into the anaesthetic record), grouped into daytime (07:30–17:59); evening (18:00–23:59); and overnight (00:00–07:29)
- Surgical specialty
- Surgical severity (minor; intermediate; major)
- Location of procedure: within or outside the main operating theatre complex (including stand-alone day surgery units), used to identify "remote-site anaesthesia".
- Grade of anaesthetist managing airway (initial airway manager and second airway manager if required)
- PPE worn by anaesthetist managing airway:
 - Eye protection: visor; goggles; other

- Respiratory protection: surgical mask; disposable FFP2/3 mask; re-usable FFP2/3 mask; powered air-purifying respirator; other

- Body protection: plastic apron; long-sleeved gown; hazmat suit; other
- Gloves: single pair; double pair; other
- Airway management technique- pre-oxygenation, mask ventilation, apnoeic oxygenation
- Airway equipment utilised to maintain oxygenation and facilitate anaesthesia, divided into:

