 - Airway devices utilised: facemask, supraglottic airway device; tracheal tube; other (including rigid bronchoscope, jet ventilator and transnasal humidified rapid-insufflation ventilatory exchange)
 - Airway techniques including: direct laryngoscopy; videolaryngoscopy; use of a flexible bronchoscope over which a tracheal tube is passed, categorised into whether performed awake or asleep
 - Use of cricoid force?

- Adjunct equipment including: bougie; stylet; Oxford or HELP pillow; high and lowflow nasal cannulae; aerosol boxes or drapes; as well as a free text option for other potential equipment

- Patient COVID-19 status:
 - Positive: RT-PCR or lateral flow test positive for SARS-CoV-2; OR symptoms consistent with COVID-19 with no SARS-CoV-2 test available; OR recent exposure to SARS-CoV-2
 - Negative: RT-PCR or lateral flow test negative for SARS-CoV-2 infection; AND actively cohorted with other COVID-19 negative patients for the entirety of their hospital stay prior to this operation; AND self-isolated according to institutional guidelines.
 - Unclear: No SARS-CoV-2 result available with no risk factors; OR not self-isolated according to institutional guidelines; OR not in a COVID-19-free pathway.
- Whether anaesthesia was terminated at the end of the procedure with a plan to wake up the patient (emergence from anaesthesia).

Airway complications:

- Number of tracheal intubation attempts.
 An attempt is defined by the number of times the laryngoscopy device is inserted or reinserted into the patient's airway.
- Best grade of laryngoscopy: modified Cormack and Lehane grading [9] into 1, 2a, 2b, 3 and 4.
- The following complications categorised into induction and emergence (defined as the period around the time of cessation of anaesthesia until hand over of patient to recovery/intensive care staff):
 - Airway trauma: evidence of airway bleeding or oedema.
 - Dental injury (arising solely from anaesthetic, rather than surgical, interventions)
 - Lip and mucosal injuries (arising solely from anaesthetic, rather than surgical, interventions)
 - Pulmonary aspiration: inhalation of oropharyngeal or gastric contents into the larynx and lower respiratory tract [10]
 - Change of intubation device: use of an additional airway device, e.g. change from supraglottic airway to tracheal tube, change from direct to videolaryngoscopy (or vice versa), use of bougie if not initially anticipated, change in type of laryngoscope e.g. McCoy vs Macintosh blade

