Shaw *et al.* [12] reported an incidence of 91 airway complications in 1874 patients (~5%). Therefore, assuming an anticipated 5% incidence of our primary outcome in our study population, a desired error of +/-1% (absolute error) of our estimate for the incidence, and a 95% confidence level of achieving the desired estimate precision, we calculate the sample size required for our study to be \geq 1822 patients (Appendix 4; [13]). For a conservative estimate, with 50 centres each performing 18 procedures a day, we expect 3600 patients to be included, allowing acceptable rates of detection of rare events.

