10.2 Statistical analysis

Incidence of airway complications amongst the sampled population will be reported as a composite of airway complications as mentioned in **Section 9**.

Continuous data will be reported using means (standard deviation, SD) or medians (interquartile ranges [range]) where appropriate. Categorical data will be reported as numbers (percentages, %) with 95% confidence intervals (CI) calculated using an appropriate method, where applicable. A p value of < 0.05 will be considered as statistically significant. Relationships between categorical variables and outcome measures will be presented as univariate odds ratios with accompanying p-values (Pearson's Chi-square test with Yates' continuity correction). Univariable logistic regression models will be fitted to investigate potential associations between variables describing patient, operator or procedural characteristics and the primary outcome of incidence of airway complications. A multivariable logistic regression model will then be fitted to include all covariates to obtain adjusted association estimates. Variables included in the regression modelling will be selected based on scientific and clinical plausibility of affecting the outcome of airway management.

11 Ethical considerations

This study is designed as a service evaluation, and no ethical approval is expected to be required. As we are collecting routinely captured data with no patient identifiable data, and will not involve either direct patient contact or influence their care in any way, no patient consent will be required. Approval from the Caldicott Guardian at the lead site (Guy's and St. Thomas' NHS Foundation Trust, London, UK), and audit registration at all recruiting centres will be required prior to commencing the project. Participating hospitals will ensure that their local investigators will be appropriately trained, but no GCP certification will be required from investigating teams as this is a service evaluation. The local PI will ensure that no patient identifiable information will be stored during the study.

12 Financing and Insurance

No funding will be required for this study. All investigators will be NHS employees working in their respective trusts and standard NHS Indemnity will apply.

13 Reporting and dissemination

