15.4 Appendix 4 – Sample Size Calculation

Sample Size for Frequency in a Population

Population size(for finite population correction factor or fpc)(N):	1000000
Hypothesized % frequency of outcome factor in the population (p):	5%+/-1
Confidence limits as % of 100(absolute +/- %)(d):	1%
Design effect (for cluster surveys-DEFF):	1

Sample Size(n) for Various Confidence Levels

Confidence	Level(%)	Sample Size
95%		1822
80%		780
90%		1284
97%		2232
99%		3142
99.9%		5117
99.99%		7142

Equation

Sample size *n* = [DEFF*Np(1-p)]/ [(d²/Z²_{1-q/2}*(N-1)+p*(1-p)]

where

n = sample size

DEFF = design effect from clustered data

N = population size (assumed to be 1 million)

p = the estimated proportion

d = the desired absolute precision

 $1-\alpha$ = the desired confidence level

Z = the Z-score for the corresponding confidence level (normally 1.96 for a 95% confidence level)

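### Section 10.2 names no hospital term, so the odds ratios for aerosol precautions and COVID-19 status may carry between-hospital differences

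*Protocol*

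**What the plan says.** Protocol Section 10.2 sets out the association analysis in three steps: univariate odds ratios with a Yates-corrected Pearson chi-square test; univariable logistic models for "potential associations between variables describing patient, operator or procedural characteristics and the primary outcome"; and one multivariable logistic model containing all covariates, chosen for their plausible influence on airway outcome. No step mentions hospital as a covariate, stratum or random effect. These analyses serve Aim 2 (Section 5) and the secondary outcomes on bundle components and COVID-19 status (Section 6.1).

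The data to account for hospital exist. Section 9.1 lists "Site (automatically populated dependent upon the login credentials of the local investigator" among the items collected for each case.

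Several provisions let hospitals differ:

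- **COVID-19 status (Section 9.1).** Negative requires self-isolation under the institution's rules, together with a negative test and cohorting. Unclear includes the clause "OR not self-isolated according to institutional guidelines" and also covers patients outside a COVID-free pathway.
- **PPE (Section 4).** Positive and unknown-status patients call for aerosol-level PPE; negative patients call for droplet-level PPE.
- **Study week (Sections 6.1 and 9.1).** Each site picks one of five weeks, so calendar week is fixed within a site.
- **Case finding (Section 8.1).** "Patients will be identified as eligible by local investigators using methods specific to the centre".
- **Outcome recording (Section 9.1).** The treating anaesthetist or assistant completes the form, and checking is done locally.

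**The concern.** If hospital influences both who is exposed and how often complications occur or are recorded, an odds ratio pooled over some 50 hospitals combines the within-hospital association with the difference between hospitals. Suppose hospitals where more cases are managed with aerosol precautions also treat harder cases or record complications more fully. The pooled odds ratio would then show precautions as harmful with no such association inside any hospital. With the opposite pattern they would look protective.

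This concerns the point estimate. It is separate from intervals being too narrow because of clustering: a design effect or cluster-robust standard errors would widen the interval around the same shifted odds ratio. At stake is the identification of bundle components associated with complications, and the comparison by COVID-19 status.

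**Working it through.** **1. The protocol's own figure.** Section 10.1 starts from "assuming an anticipated 5% incidence of our primary outcome in our study population". It asks for a precision of one percentage point either way, at two-sided 95% confidence. Appendix 4 adds "N = population size (assumed to be 1 million" and a design effect of 1. The Appendix 4 formula is n = DEFF·N·p(1−p) / [(d²/z²)(N−1) + p(1−p)]. With p = 0.05, d = 0.01, z = 1.96, N = 1,000,000 and DEFF = 1 it gives 1821.4, rounded up to 1822, as stated. The expected total also reproduces: 50 × 18 × 4 = 3600, or 72 per hospital. At 5% that is 72 × 0.05 = 3.6 events per hospital. These figures concern incidence. The protocol gives none for the association analyses, nor for between-hospital variation, so the inputs below are assumptions.

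**2. Exact two-group check.** Take two equal groups of hospitals with exposure proportions e₁, e₂ and complication risks r₁, r₂. Within each hospital exposure has no effect (odds ratio 1). The pooled cells are proportional to:

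- exposed with event: a = e₁r₁ + e₂r₂
- exposed without event: b = e₁(1−r₁) + e₂(1−r₂)
- unexposed with event: c = (1−e₁)r₁ + (1−e₂)r₂
- unexposed without event: d = (1−e₁)(1−r₁) + (1−e₂)(1−r₂)

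For exposure 20% v 60% and risk 4% v 6%: a = 0.044, b = 0.756, c = 0.056, d = 1.144, so the pooled OR = (0.044 × 1.144)/(0.756 × 0.056) = 1.19. Similarly:

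| Exposure | Risk | Pooled OR | Risks swapped |
|---|---|---|---|
| 20% v 40% | 4% v 6% | 1.10 | 0.90 |
| 20% v 60% | 4% v 6% | 1.19 | 0.84 |
| 20% v 60% | 3% v 7% | 1.41 | 0.69 |
| 20% v 20% | any of these | 1.00 | 1.00 |
| any of these | 5% v 5% | 1.00 | 1.00 |

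Bias needs both exposure and risk to differ between hospitals. A more extreme contrast (10% v 70%, 3% v 7%) gives 1.67 or 0.57; the conclusion does not rely on it.

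**3. Simulation.** 50 hospitals × 72 patients, risk about 5%, exposure about one third, true within-hospital OR 1. Hospital effects on exposure and risk are normal on the logit scale with the SDs and correlation shown. The pooled test is the protocol's Yates chi-square; the comparator is Mantel-Haenszel stratified by site.

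| SD exposure | SD risk | Correlation | Pooled OR | False positives | Stratified OR | False positives |
|---|---|---|---|---|---|---|
| 1.0 | 0.4 | 0.25 | 1.08 | 8% | 0.99 | 5% |
| 1.0 | 0.3 | 0.5 | 1.12 | 12% | 1.00 | 4% |
| 1.0 | 0.5 | 0.5 | 1.22 | 28% | 1.00 | 5% |
| 1.0 | 0.6 | 0.5 | 1.27 | 33% | 1.00 | 4% |
| 1.5 | 0.6 | 0.5 | 1.36 | 48% | 1.00 | 5% |
| 1.0 | 0.6 | −0.5 | 0.78 | 26% | 1.00 | – |
| 1.0 | 0.5 | 0 | 0.99 | 7% | 0.99 | 6% |

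A separate simulation without the Yates correction gave pooled ORs of 1.08 to 1.35 for positive correlations of 0.25 to 0.5, and 0.73 to 0.85 at −0.5. For the positive correlations, false positives were 10 to 49%, still 9 to 39% with cluster-robust errors. Its example at SDs 1.0 and 0.6, correlation 0.5, had standard errors of 0.161 pooled and 0.179 stratified: 0.179/0.161 = 1.11, about 11% larger.

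No run includes patient covariates. The results describe the crude odds ratio only.

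**The case against.** The strongest reply is that much of this rests on silence. Section 10.2 does not exclude site, its plausibility rule for covariates would admit a hospital term, and a statistical analysis plan not seen here could add one. For the multivariable model that stands: a reader might infer that site is ruled out, and the text does not say so. It does not rescue the crude step, where the covariate rule has no bearing on an unstratified chi-square odds ratio.

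Second, a reader might infer that COVID-19 status as a whole follows each hospital's rules. It does not. Positive has one definition at all sites, and Negative also needs a negative test. The explicit institutional rule acts on the Negative/Unclear boundary, so contrasts with Positive are affected mainly through the comparator and hospital case-mix. Nor does the protocol describe hospital-specific precaution policies; the link to PPE runs through status.

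Third, a reader might infer that centre-specific case finding biases the odds ratios. Alone it does not: Section 8.1 expects operating lists and theatre bookings to be used, seeks every eligible patient where possible, and Section 9.2 records the capture rate. Outcome definitions are also common to all sites, many of them objective.

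Fourth, the planned patient, operator and procedural covariates could absorb much of any case-mix difference. This stands. So does the point that the mild setting is small: ln 1.08 = 0.077, about half the example standard error of 0.161.

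Finally, within a hospital PPE varies with patient status, so conditioning on site can concentrate confounding by indication. With about 3.6 events per hospital, within-hospital estimates should not be the only result shown.

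**Conclusion.** The point holds as a risk to the association analyses. The protocol specifies pooled odds ratios and logistic models without naming a hospital term, while its own provisions make hospital a plausible influence on exposure and on case-mix or recorded complications. A reader might conclude that the odds ratios will mix hospital effects with those of precautions or infection. The documents do not support that, because bias needs exposure and risk to vary together across hospitals and no figure is given for either.

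Under the assumed ranges, the crude pooled odds ratio is about 1.1 to 1.4, or 0.7 to 0.9 with the correlation reversed, when the within-hospital value is 1. False positives are about 8 to 49%. At zero correlation the odds ratio is unbiased. Bias after covariate adjustment was not simulated and could be smaller. Aim 2 and the COVID-19 secondary outcome are affected; this mechanism does not touch overall incidence, the primary outcome. The change is worth making because the remedy is cheap and the data are already collected.

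**What to change.** Amend Section 10.2 as follows.

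- **Crude associations:** give Mantel-Haenszel odds ratios stratified by site beside the unstratified ones, and keep the unstratified ones as descriptive results.
- **Adjusted associations:** account for site in the multivariable model in one of two ways. One is a site random intercept plus the site mean of the exposure, which separates within- from between-hospital associations; a random intercept alone separates them only in part. The other is conditional logistic regression with site as stratum.

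Since each site contributes one week, stratifying by site also removes differences between study weeks.

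The cost is wording and analysis time, with no new data. Intervals become somewhat wider: in the simulations the stratified estimate was roughly 5 to 20% less precise, at an assumed exposure of about one third. A precaution used for every case in a hospital, or for none, gives no within-hospital information there. The number of hospitals contributing to each comparison should therefore be reported.

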6.1 Study Design

AeroComp is service evaluation exploring the incidence of airway complications amongst patients undergoing general anaesthesia for surgical procedures within NHS Trusts. All adult patients undergoing any surgical procedure (with the exception of obstetric procedures) with the primary method of anaesthesia planned to be general anaesthesia will be eligible for enrolment to this study. The study duration will encompass 5 days (patients being enrolled over a 96 hour consecutive window with a further day of follow-up data collection) with an estimated total of 3600 patients being included. Individual sites are free to choose their own data collection window between 1st November

2021 and 3rd December 2021 as long as the 96 hour window commences at 07:30 on a Monday and closes at 07:29 on a Friday.

Primary outcome:

 Incidence of airway complications at both induction and emergence, defined as a composite of: airway trauma, aspiration, dental/lip/mucosal injury, change of intubation device, desaturation, three or more laryngoscopy attempts, grade 3 or 4 laryngoscopy, difficult face mask ventilation, difficult supraglottic airway device (SAD) usage, emergency front-of-neck airway, failed tracheal intubation, laryngospasm, oesophageal intubation (immediate or delayed recognition), requirement of reintubation immediately after extubation, and need for second intubator.

Secondary outcomes:

- Risk of composite outcome of airway complications will be reported for each individual component of the aerosol precaution bundle.
- Individual complications that comprise the primary outcome.
- Subjective operator assessment of airway difficulty
- Unanticipated airway difficulties necessitating significant deviation from the original airway plan.
- Composite risk of airway complication and association with confirmed/suspected COVID-19 infection, known negative COVID-19 infection without any potential COVID-19 risks, and all other patients.

7 List selection

Operating lists from all participating NHS hospitals will be included, with patients from those lists being eligible. Both elective and emergency cases will be included. The centres and local investigators will be identified by the Pan-London Perioperative Audit and Research Network (PLAN) or other national trainee research networks.

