7.1 Patient inclusion criteria

- Adult patients (≥ 18 years of age)
- Undergoing a surgical, radiological or cardiological procedure (interventional or diagnostic) with the primary method of anaesthesia planned to be general anaesthesia

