Was cricoid force us		vay plan?	□ No □ No	Oesophageal intubation (recognised) ¹¹ Oesophageal intubation (delayed recognition) ¹¹ Reintubation immediately post-procedure ⁹		
Subjective ease of fa Subjective ease of S Subjective ease of tr		tempted 🗖 1 (Easy) 🗖 2	3 4 5 (Difficult) 3 4 5 (Difficult) 3 4 5 (Difficult) 5 5 (Difficult)	Second airway manager required ⁶ AeroComp Case Record Form v1.2		

AeroComp Case Record Form v1.2 Notes

- 1) The study day is defined as the time period from 07:30 on the specified day until 07:29 the following morning. Thus, if an operation commences at 04:00 on Friday morning, the "Study Day" should be Thursday, and Start Time should be 00:00 to 07:29.
- 2) Surgical urgency is defined as per NCEPOD (https://www.ncepod.org.uk/classification.html)
 - a. Immediate Immediate life, limb or organ-saving intervention resuscitation simultaneous with intervention. Normally within minutes of decision to operate.
 - b. Urgent Intervention for acute onset or clinical deterioration of potentially life-threatening conditions, for those conditions that may threaten the survival of limb or organ, for fixation of many fractures and for relief of pain or other distressing symptoms. Normally within hours of decision to operate.
 - c. Expedited Patient requiring early treatment where the condition is not an immediate threat to life, limb or organ survival. Normally within days of decision to operate.
 - d. Elective Intervention planned or booked in advance of routine admission to hospital. Timing to suit patient, hospital and staff.
- 3) Surgical severity is defined as per NICE guidance NG45 (https://www.nice.org.uk/guidance/ng45/chapter/recommendations). Examples include:
 - a. Minor Excising skin lesion, draining breast abscess.
 - b. Intermediate Primary repair of inguinal hernia, excising varicose veins in the leg, tonsillectomy or adenotonsillectomy, knee arthroscopy.
 - c. Major Total abdominal hysterectomy, endoscopic resection of prostate, lumbar discectomy, thyroidectomy, total joint replacement, lung operations, colonic resection, radical neck dissection.
- 4) Start time should be the time of the first set of observations upon the anaesthetic record.
- 5) SAS specialty and associate specialist; SCF senior clinical fellow. If no exact match is presented please choose the closest equivalent grade.

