- 6) Second airway manager: if a second individual took over management of the airway following management by the initial airway manager their grade should be recorded here and "second airway manager required" ticked within the complication section. Leave blank if not applicable.
- 7) Other: this applies to, for example, rigid bronchoscopes, jet ventilators and transnasal humidified rapid-insufflation ventilatory exchange. This should be ticked only if it was the primary airway device following induction of anaesthesia. Typically this will be a planned technique involving pre- +/- per-oxygenation following discussion with the operating surgeon beforehand. Also select if the primary means of oxygenation during the procedure is via a surgically placed jet ventilator (e.g. laryngeal procedures) and no other airway device is placed prior or subsequently by the anaesthetist. The exact device used does not have to be specified.
- 8) Tracheal intubation attempts/laryngoscopy grade should be left blank if intubation is not attempted. The grade here refers to the Cormack and Lehane system as modified by Yentis and Lee, shown below.
- 9) If the patient was not woken up at the end of surgery, emergence complications should not be recorded. If the patient was woken up and then immediately reintubated, this should be recorded as: Woken up: Yes; Reintubation immediately post-procedure: On emergence.
- 10) Only death due to hypoxia or another complication of airway management should be recorded.
- 11) Recognised oesophageal intubation is detected after the first but before the fourth ventilatory breath has been delivered. Delayed recognition is when four or more ventilatory breaths have been delivered.

	1	2		3	
Original Cormack and Lehane system	Full view of the glottis	Partial view of the glottis or arytenoids		Only epiglottis visible	Neither glottis nor epiglottis visible
View at laryngoscopy	E	Y	Y		
Modified system	1 As for original Cormack and Lehane above	2a Partial view of the glottis	2b Arytenoids or posterior part of the vocal cords only just visible	3 As for original Cormack and Lehane above	4 As for original Cormack and Lehane above

E = epiglottis, LI = laryngeal inlet. From Yentis SM, Lee DJH. (1998) Grading of direct laryngoscopy. Anesthesia. 53:1041-4.

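### Airway trauma has no exclusion for surgical causes, so bleeding or swelling from the operation itself can count toward the primary composite

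*Protocol*

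**What the plan says.** Section 6.1 gives the primary outcome as the incidence of airway complications at induction and emergence, "defined as a composite of: airway trauma, aspiration, dental/lip/mucosal injury" and further items. One component is enough to make a patient a case. Individual complications are also secondary outcomes.

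Section 9.1 defines three tissue-injury items one after another. The first reads "Airway trauma: evidence of airway bleeding or oedema" and says nothing about cause. The second does limit the cause: "Dental injury (arising solely from anaesthetic, rather than surgical, interventions". The third, on lips and mucosa, carries the same limit as the second.

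Each is recorded separately for induction and for emergence, and emergence is "defined as the period around the time of cessation of anaesthesia until hand over of patient to recovery/intensive care staff".

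Eligibility in Section 7.1 is broad: "Undergoing a surgical, radiological or cardiological procedure (interventional or diagnostic) with the primary method of anaesthesia planned to be general anaesthesia". Section 7.2 does not exclude surgery on or near the airway. The CRF in Appendix 2 offers ENT, Max-Fax and Dental among its specialties. Its notes cite "tonsillectomy or adenotonsillectomy, knee arthroscopy" as examples of intermediate surgery and mention a "surgically placed jet ventilator (e.g. laryngeal procedures".

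On the CRF, airway trauma, dental injury and lip/mucosal injury are plain tick boxes. None of the eleven notes limits the cause of any of them.

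**The concern.** The protocol recognises that surgery can produce injuries that look like airway complications, and it screens these out for teeth, lips and mucosa. It does not do so for bleeding and oedema, where an operation in the mouth, pharynx or larynx is an obvious alternative cause. A patient with blood in the airway after a tonsillectomy satisfies the definition as written.

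Two things are at stake. The main result is an incidence with a target precision of ±1 percentage point, and counting surgical events biases it upward; a larger sample does not reduce bias. Also, anaesthetists and assistants at about 50 centres must decide for themselves whether surgical blood counts, so the component may mean different things at different sites.

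**Working it through.** **1. The three definitions side by side (Section 9.1).**

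| Item | Surgical cause excluded in 9.1? | Surgical cause excluded on the CRF? |
|---|---|---|
| Airway trauma (bleeding or oedema) | No | No |
| Dental injury | Yes | No |
| Lip and mucosal injury | Yes | No |

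A mucosal wound made by the surgeon is excluded by the third row, but the bleeding from that same wound qualifies under the first. Since the composite needs only one component, the patient can still become a case, and the exclusion in the third row has no effect for that patient.

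**2. When it can happen.** Induction precedes surgery, so the problem lies mainly in the emergence column. CRF note 9 says that emergence complications are not recorded for patients who are not woken, which limits it to patients who are.

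**3. Whether it can be undone later.** No cause is recorded for airway trauma. Section 9.2 states that the name of the operation is not collected. Section 9.1 has the local ID detached once the CRF is complete, so an event cannot be traced back to the notes. Specialty is collected, but setting aside a whole specialty would also discard genuine anaesthetic trauma within it.

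**4. The plan's own figures (Section 10.1, Appendix 4).** Inputs: p = 0.05, d = 0.01, N = 1,000,000, DEFF = 1, Z = 1.96.

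n = DEFF × N × p(1 − p) / [(d²/Z²)(N − 1) + p(1 − p)] = 1821.4, rounded up to 1822 as stated.

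Expected recruitment is 50 × 18 × 4 = 3600. The 95% half-width at 5% is 1.96 × √(0.05 × 0.95 / n), which is 1.0 point at n = 1822 and 0.71 point at n = 3600. This arithmetic is sound and is not in dispute.

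**5. A yardstick for the bias.** Let s be the share of patients having surgery in the airway and b the proportion of those ticked for surgical blood or oedema. The documents give neither. If such ticks are independent of the other components and the true composite is 5%:

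observed incidence = 0.05 + 0.95 × s × b

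| s (assumed) | b (assumed) | Observed | Shift (points) |
|---|---|---|---|
| 5% | 5% | 5.2% | 0.2 |
| 10% | 20% | 6.9% | 1.9 |
| 15% | 50% | 12.1% | 7.1 |

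The shift reaches one point when s × b = 0.01 / 0.95 = 1.05% of all patients, which is 0.0105 × 3600 ≈ 38 patients. The table shows only that the effect could be trivial or large; it is not an estimate.

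**The case against.** The strongest reply is that the wider wording may be deliberate. Section 4 names airway oedema as a suspected complication in SARS-CoV-2 patients and says the virus itself may be a risk factor. Section 6.1 makes the association of the composite with COVID-19 status a secondary outcome. Airway trauma is the only listed item that captures oedema. Copying the neighbouring qualifier, which admits only anaesthetic causes, would drop disease-related oedema and damage that outcome. This stands, and it determines the form of the fix. It does not explain why bleeding from the operation should count.

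A second reply is that aspiration, laryngospasm, desaturation and reintubation carry no causal limit either, so counting perioperative events regardless of cause is a design choice. That is fair for those items. For tissue injury, though, the protocol itself chose to exclude surgical causes in two of three cases.

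A reader might infer that every case of surgical blood must be ticked, so that inflation is certain. The text does not support this. The item is called trauma and sits under a heading of complications, so some anaesthetists will leave out expected blood in the operative field. What follows is possible upward bias together with inconsistent classification.

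A reader might also infer that the associations with aerosol precautions are confounded. Nothing in the protocol shows that PPE or device choice differs by specialty, and Section 10.2 allows procedural characteristics in the multivariable model. That claim is not made here.

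**Conclusion.** The point holds as a gap in the definition of a primary-outcome component. As written, bleeding or oedema caused by the operation qualifies as airway trauma at emergence, eligible procedures make this foreseeable, and no other section or CRF note closes the gap. The direction of any bias in the incidence is upward, with uneven ticking across sites as a second consequence.

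The size cannot be determined from the documents. A reader might want to attach a range of percentage points to it, but any such range rests wholly on assumed case mix and assumed ticking. The firmest statement available is the yardstick of about 38 patients in 3600 per point of shift, under independence from the other components and a true incidence of 5%. The sample size calculation is unaffected. Because cause and operation are not recorded, the remedy has to come at data capture; a sensitivity analysis by specialty would be only rough.

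**What to change.** In Section 9.1, keep the present definition of airway trauma and add: *excluding that caused by the surgical procedure itself*. This removes operative blood and swelling while oedema due to disease, including COVID-19, still counts.

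Add one numbered note to the CRF in Appendix 2 stating the surgical-cause exclusion for airway trauma, dental injury and lip/mucosal injury together. A note on airway trauma alone would create a new asymmetry on the form.

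The cost is one phrase and one note, with no new data field. The small downside is that the anaesthetist must judge cause when it is mixed, as Section 9.1 already requires for the two neighbouring items.
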